10.0 Statistical Analysis and Data Management

Analytic Strategy.

Power and sample size. The proposed study is powered to detect a meaningful difference in end of treatment tobacco abstinence between cannabis co-users and tobacco only users. Secondarily, the study will assess the relationship between cannabis use patterns during treatment and nicotine dependence severity in co-users. Specific Aim #1: Examine the impact of cannabis co-use on tobacco cessation outcomes among co-users compared to tobacco only users. Hypothesis 1: Co-users will have lower rates of 7-day point prevalence abstinence from tobacco at the end of treatment (Week 12) compared to tobacco only users. In a cross-sectional survey of national household data (51), tobacco cessation was reported among 65.5% of respondents who endorsed no cannabis use as compared to 21.8% of tobacco cessation in those reporting current cannabis use ($\Delta=43\%$). Studies examining the efficacy of varenicline for tobacco cessation (108, 109) noted near 50%-point prevalence abstinence at treatment conclusion (Week 12) in the varenicline-treated group. Finally, in our recently completed adolescent varenicline trial (U01 DA0317779), youth cannabis co-users reported point prevalence tobacco abstinence in 20% of participants at Week 12 and 43% in those who use tobacco only (analysis with all available data). The proposed R01 study intends to apply a successful tobacco treatment (varenicline) paired with contingency management in treatment-seeking smokers. Assuming a similar abstinence rate in tobacco only users (45%) and a successful abstinence rate in participants who are cannabis co-users as compared to the adolescent study (20%; $\Delta=25\%$), to achieve 80% power with a 5% type 1 error rate, a sample of 82 participants in the cannabis co-using cohort and 41 in the tobacco only cohort. However, to account for the inclusion of 2 study sites in the design, an additional fixed factor of site will be included in the analytic models. Although we hope that equal proportions of co-users and non co-users present at each site, we understand that the fundamental differences between the Charleston metro area, Pickens County SC, and Florence exist and may cause some correlation between co-use group and study site. Assuming that the proportion of variance in co-use groups due to study site and other covariates may be moderate ($R^2=0.25$) and that attrition will not exceed 25%, we have adjusted our study sample size to account for this scenario. This increases our randomized sample to a total of 208 (139 cannabis co-users and 69 tobacco only users) accounting for both site correlations with co-use group and anticipated attrition. If site correlations with study outcomes or attrition are lower than pre-specified, our statistical power will exceed 80%. Specific Aim #2: Among co-users, assess changes in cannabis use during tobacco cessation treatment. Hypothesis 2: Co-users with moderate to high severity of nicotine dependence will demonstrate increases in concurrent cannabis use, while lower severity of nicotine dependence will yield no changes in cannabis use. To attain adequate power to assess Aim #2, a within co-use cohort comparison, the study will oversample the cannabis co-use cohort as compared to the tobacco only cohort (2:1). At screening, nicotine dependence will be assessed via the Fagerström Test for Nicotine Dependence (FTND) (92) and categorized accordingly: low nicotine dependence (0-4), medium or high nicotine dependence (5-6; 7-10). Cannabis use during the final 4 weeks of study treatment as compared to baseline use will be assessed among co-users. Based on our preliminary data from an ongoing adult tobacco cessation trial (R34 DA042228), we have nearly equivalent numbers of participants falling into low and moderate/high nicotine dependence categorizations (Mean=4.5; Median=5). Therefore, we anticipate ~40% will have medium/high nicotine dependence. With 208 participants, 139 in the cannabis co-use cohort (104 completers), we will achieve 80% power with a type 1 error rate of 5% to detect a between group cannabis use difference of Cohen's $d\approx0.6$ (Med/High nicotine dependence vs. low nicotine dependence).

Statistical analyses. Demographic, clinical and substance use characteristics will be collected at baseline and tabulated for the overall study cohort and between study groups. Categorical variables will be assessed between groups by chi-square tests of independence, while continuous variables will be assessed using Student's t-test. In addition to baseline group differences, preliminary analysis of baseline characteristics with tobacco use outcomes of interest will examine significant correlates of abstinence in the study population.

Propensity Score Methods: Both cannabis co-using cigarette smokers and tobacco only smokers will be recruited in a 2:1 allocation and all participants will receive varenicline, contingency management, and

psychosocial counseling. Non-randomized trials often suffer from inherent selection bias due to systematic baseline differences in study populations (110). The use of propensity scores has been shown to reduce selection bias and increase parameter estimate precision in non-random designs better than traditional covariate adjustment (111). In the proposed study population, we anticipate a mild, yet systematic difference in baseline factors between cannabis co-users and tobacco only users. Specifically, we expect that age and race (112) may be substantially imbalanced as well as baseline severity of tobacco use and nicotine dependence. To account for such differences, augmented inverse probability of treatment weighting using the propensity score (AIPW) methods will be used to account for observed covariate values (113). This methodology will provide unbiased parameter estimates and standard errors of the average treatment effect even when either the propensity model or outcome model is mis-specified (doubly robust) (114). All observed variables that may potentially influence the self-selection into the co-use group will be included into the calculation of the propensity score (gender, education, motivation to quit, nicotine dependence, social influences, etc.). Prior to model analysis, weighted means of the measured baseline characteristics will be assessed between groups to assess balance. Additionally, weights will be checked for values close to either zero or one and adjustments to the probability model will be made when necessary. Augmented propensity score weighting strategies (AIPW) were chosen as the primary analytic approach as opposed to matching or stratification such that all study participants will be retained in the final analysis and statistical power would be preserved with the proposed sample size.

Primary Study Aims: Aim 1: To assess the difference in the log-odds of abstinence from tobacco at the end of treatment (Week 12) between baseline cannabis co-users compared to tobacco only participants, augmented inverse probability weighted logistic regression models will be developed. The inverse of the conditional probability of being in the cannabis co-use cohort will be included in the model to account for inherent imbalances between study groups and to reduce bias by resembling a randomized controlled trial. In addition to the inverse propensity weights, AIPW methods incorporate a covariate and study site adjusted model for the study group outcome (114). Aim 2: To assess the association of baseline nicotine dependence severity (Med/High nicotine dependence vs. low nicotine dependence) with cannabis use rates during study treatment, generalized linear mixed effects models will be assessed with cannabis use rates and amounts during the final 4 weeks of treatment as the primary indicator of cannabis use severity and nicotine dependence group as the primary model predictor. In addition to grouping by nicotine dependence severity, continuous levels of dependence severity (FTND score) will be modeled to assess possible linear and quadratic relationships between dependence severity and cannabis use. Following examination of the differences in end of treatment cannabis use rates based on baseline nicotine dependence, rates of cannabis use will be assessed by group (nicotine dependence severity) over all weekly study visits to determine if those with increased dependence severity exhibit a different trajectory (slope and pattern) of cannabis use during the entire study treatment. Model-based means and associated standard errors will be used to test group level differences. Exploratory Aim: To assess the relationship between baseline cannabis use severity and tobacco outcomes, generalized linear mixed effects models will be developed with weekly 7-day point prevalence abstinence from tobacco as the primary model outcome. In addition to tobacco abstinence, weekly average cigarettes per day will be examined as an indicator of use reduction differences over time. Longitudinal patterns in tobacco abstinence and use amounts will be modeled through the inclusion of baseline cannabis use severity indicators, study visit, and baseline tobacco use rates as model covariates. Additionally, differential effects over time will be examined with the inclusion of the interaction of cannabis use severity and study visit. Model-based means and associated standard errors will be used to test group level differences across the study treatment.

Secondary Data Analysis: In addition to end of treatment point prevalence tobacco abstinence rates, similar analytic models will be used to assess abstinence rates at the 6-month follow-up visit. Additionally, longitudinal analysis of weekly tobacco abstinence will be assessed using repeated measures logistic regression models using a general estimating equations framework (GEE) (115) and working correlation

structures will be independently compared using the quasi-likelihood under the independence model criterion statistic (116). Similarly, the number of smoking days per week and cigarettes per day will be collected via daily diaries and compared between co-use cohorts using generalized linear mixed effects regression models. Finally, weekly cannabis and tobacco use will be collected to develop group-based trajectory models and time naïve covariates will be used to determine group membership. Additionally, changes in cannabis craving, withdrawal, use, and subjective effects during treatment with varenicline will be examined in the cannabis co-use group. Specifically, changes in cannabis craving, withdrawal (synchronous effects of varenicline) and cannabis use severity (substitution) will be assessed for correlations with changes in tobacco use. Generalized linear mixed effects models will be developed with cannabis use outcomes and the time varying effects of tobacco use as the primary independent variable. Further, noting possible differences in the relationship between tobacco outcomes and combustible/non-combustible cannabis use, model effect modification will be assessed using cannabis use type groupings (primarily combustible vs. primarily non-combustible). All analyses will be conducted using SAS version 9.4 (SAS Institute, Cary, NC, USA).

Missing data and attrition. The study team has procedures in place to minimize missing data and attrition (e.g., reminders, compensation, updated and detailed locator information, etc.); however, these methods do not ensure that all data will be collected. Appropriate analysis methods will be employed to accommodate missing data. Methods of maximum likelihood yield valid inferences assuming ignorable attrition (i.e., attrition is accounted for by covariates or the dependent variable measured prior to dropout). In addition, in keeping with the Intent to Treat Principle, we will make every effort to continue assessments for the entire course of treatment, even among those who stop participating in study procedures.

Data Management. Data will be collected by trained and approved research staff and will only be identified with the study's ID of the participant. The codes linking the name of the participant to the study ID will be kept confidential in a secured cabinet or password-protected data file. Collected study forms will be kept within the office suite of the PI and research staff (Charleston) and within research office suites at participating sites and will not be taken outside of any office buildings. Research staff will enter data into a database management system maintained by MUSC, Research Electronic Data Capture (REDCap). REDCap is a secure, web-based application designed exclusively to support data capture for research studies. These procedures are effective in minimizing data entry errors (e.g., missing or errant data). Direct entry of data by study participants (self-reports) will also be conducted in this study. This is done through a front-end survey interface that allows the participant to enter data on select questionnaires/assessments, but not access any other study records or data in REDCap. A REDCap survey link will be used to collect mobile daily diaries and videos of medication dosing, which are immediately transmitted into REDCap with de-identified subject IDs. Videos are uploaded and stored within REDCap, and not the user's device. Server maintenance will be conducted by Information Technology Specialists at MUSC. The PILSY platform will house PHI (email and phone number) that is necessary to setup a participant with a smart cap. PILSY has been vetted by MUSC IS and is approved to house data. The platform is password protected and only accessible by study team members.

For EMA data collection in ilumivu, participants will be assigned a deidentified subject ID, which study staff will keep confidential in a secured cabinet or password-protected data file. After each participant installs the ilumivu app on their personal mobile phone, they will enter a unique code and the app downloads surveys and survey schedules for the participant. Once information is downloaded to the participant's phone, the app is operated offline with no connections to the ilumivu server. Periodically, participants are asked to click a synchronization button to upload the collected data to a secure server. All data are encrypted before being transmitted to the cloud-based storage database. The data are stored in a MariaDB database where the only identifying information associating it with the participant is the unique randomly generated code. Access to the database is gated; entry is only permitted to users entering through the approved route

(cannot be accessed by guessing the URL). Ilumivu, Inc. is an approved vendor with MUSC and is being used with other study protocols. MUSC and ilumivu have signed a terms and conditions document to assure data protection and privacy.

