B1. Study Overview. This proposed prospective tobacco cessation study will evaluate the impact of concurrent cannabis use and severity on tobacco abstinence among co-users and assess changes in cannabis use during treatment. Adult tobacco users (ages 18-40) who are motivated to quit smoking will be recruited. Cannabis co-users will be oversampled (2:1) and will be compared to tobacco only participants (using appropriate propensity score models). All participants will receive first-line tobacco cessation pharmacotherapy (varenicline) paired with a behavioral intervention to bolster abstinence rates (contingency management and psychosocial counseling) for a standard 12-week treatment period. Cannabis use will not be targeted with treatment. This is not a treatment outcome study per se and thus we are not evaluating (with a control group) an intervention. Rather, cannabis use status (co-use vs. not) is our independent variable. Biochemical verification of tobacco and cannabis use will be collected at screening and throughout the 12-week treatment period in addition to daily self-reports of use. Specifically, this study will: 1) examine the impact of cannabis co-use on tobacco cessation among co-users compared to tobacco only users (Aim #1); 2) with the use of frequent measurement, assess changes in cannabis use (among co-users) during tobacco treatment and determine if profiles of changes in cannabis use emerge (i.e., compensatory use, reduction, no change) (Aim #2); and 3) assess for a dose-dependent impact of cannabis use severity on tobacco cessation outcomes among co-users (Exploratory Aim).

It should be noted that while this is not a randomized and blinded study (cannabis co-use status will be known to research staff), it is important to not bias the results of the study. The hypothesis is that cannabis co-use will adversely impact tobacco cessation, but it's important to the scientific integrity of this study to obscure that hypothesis from study participants and manage biases with research staff. Staff will be educated about introducing bias into the study and methods to manage bias in non-randomized and non-blinded trials. For research participants, the aim of the study will intentionally broad and ambiguous to not

overtly influence their behavior and tobacco quit attempt. The title of the study and consent document, therefore, are not as specific as they would normally be to maintain the integrity of this research.

B2. Preliminary Studies.

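### Double robustness does not make the usual AIPW standard error correct, and the plan names no other variance method for the Week 12 comparison

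*Combined protocol and SAP*

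**What the plan says.** Under Propensity Score Methods in section 10.0, the plan says of AIPW: "This methodology will provide unbiased parameter estimates and standard errors of the average treatment effect", and adds that this holds if the propensity model or the outcome model is wrong. The claim is conditional: one of the two models may be wrong, not both. It covers the standard errors as well as the estimates.

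The same paragraph limits the adjustment to measured variables: AIPW "methods will be used to account for observed covariate values". The propensity covariates are an open list ("gender, education, motivation to quit, nicotine dependence, social influences, etc"). Two diagnostics are planned. One is balance: "weighted means of the measured baseline characteristics will be assessed between groups to assess balance". The other concerns extreme values: "weights will be checked for values close to either zero or one and adjustments to the probability model will be made when necessary".

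Under Primary Study Aims, Aim 1 is a difference in log-odds of Week 12 abstinence from an AIPW logistic model, with weighting intended "to reduce bias by resembling a randomized controlled trial". Section 2.0 (Study Overview) acknowledges that "this is not a randomized and blinded study".

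Section 10.0 does not say how the AIPW standard error will be computed, does not state the no-unmeasured-confounding assumption, and plans no sensitivity analysis for it.

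**The concern.** The sentence joins two properties. The first, protection of the point estimate when one model is wrong, is what double robustness provides, in large samples and with all confounders measured. The second, a correct standard error under the same condition, does not follow. The usual AIPW standard error is built from the estimated influence function. It treats the fitted propensity and outcome models as if both were right, and it can be wrong when one is not. In a sample of this size it can also be somewhat small when both are right.

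At stake are the interval and test for Aim 1. If the statement is taken at face value, an analyst has no reason to look beyond the default standard error, and the nominal 95% interval may not cover at 95%. A reader told that the estimate is unbiased is also not told that this depends on no unmeasured confounding, which the planned diagnostics cannot examine.

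**Working it through.** **Planning figures.** From section 10.0: abstinence 45% (tobacco only) and 20% (co-users), 2:1 allocation, 80% power, 5% type 1 error (taken as two-sided). With unpooled variance the smaller group needs (1.960 + 0.842)² × (0.45×0.55 + 0.20×0.80/2) / 0.25² = 7.85 × 0.3275 / 0.0625 = 41.1, or about 123 in total, which reproduces the printed 41 + 82. The final 208 (139 + 69) is used as printed. With 25% attrition, 208 × 0.75 = 156, about 104 and 52.

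**Simulation of the standard error.** The settings are assumptions, not document figures. There were six measured covariates with one interaction and one squared term, about two thirds exposed, and true abstinence of 23% vs 47% (stronger confounding, R² of exposure about 0.16) or 20% vs 46% (weaker, about 0.05). Both R² values are below the plan's 0.25. A wrong model omits two confounders and the nonlinear terms. Results are on the risk-difference scale at n = 208 with 2,000 runs per row. The Monte Carlo error of coverage is about √(0.92×0.08/2000) = 0.6 points.

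| Setting | Wrong model | Bias | Mean SE | True SD | Ratio | Coverage |
|---|---|---|---|---|---|---|
| Stronger | none | +0.001 | 0.070 | 0.076 | 0.92 | 91.8% |
| Stronger | propensity | -0.001 | 0.064 | 0.073 | 0.88 | 90.8% |
| Stronger | outcome | -0.011 | 0.087 | 0.083 | 1.05 | 95.5% |
| Stronger | both | -0.126 | 0.068 | 0.070 | 0.97 | 53.2% |
| Weaker | none | +0.003 | 0.070 | 0.073 | 0.96 | 92.6% |
| Weaker | propensity | +0.002 | 0.067 | 0.072 | 0.93 | 92.2% |
| Weaker | outcome | 0.000 | 0.074 | 0.074 | 1.00 | 94.2% |
| Weaker | both | -0.039 | 0.069 | 0.070 | 0.99 | 89.8% |

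A separate run, also under assumed settings, agreed:
- Propensity model wrong: 0.065 against 0.074 at n = 208 (91%) and 0.074 against 0.084 at n = 156 (92%), both ratio 0.88.
- Outcome model wrong: 0.079 against 0.075 (ratio 1.05, 96%).
- Both models right: coverage about 93%.

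On the log-odds scale, which Aim 1 uses, coverage at n = 208 in the stronger setting was 92.9% (neither wrong), 90.9% (propensity wrong) and 96.4% (outcome wrong). At n = 5,000 with the propensity model wrong, the log-odds SE was still 0.060 against 0.066, about 10% too small, so that part is not only a small-sample effect.

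**Bootstrap, refitting both models.** This used the propensity-wrong case at n = 208, with 300 datasets and 120 resamples each. In the stronger setting the mean SE was 0.073 against a true SD of 0.073, and coverage was 94% against 90% for the influence-function SE on the same datasets. In the weaker setting coverage was 96% against 94%. Monte Carlo error is about 1.5 points.

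**Unmeasured confounding.** With both models right for the measured covariates, an assumed standard-normal confounder with log-odds ratios of 0.5 (exposure) and -0.5 (outcome) gave a bias of -0.04 and 89% coverage at n = 208.

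**E-value for the planned effect.** RR = 0.45/0.20 = 2.25, and E = RR + √(RR(RR-1)) = 2.25 + √(2.25×1.25) = 3.93. For the confidence limit nearest the null:
- 52 vs 104 analysed: SE(log RR) = √(0.55/23.4 + 0.80/20.8) = 0.249, limit = exp(0.811 - 1.96×0.249) = 1.38, E = 2.11. With the variance divided by 1 - 0.25: SE 0.287, limit 1.28, E = 1.88.
- 69 vs 139 analysed: SE = √(0.55/31.05 + 0.80/27.8) = 0.216, limit 1.47, E = 2.31. With the same inflation: SE 0.249, limit 1.38, E = 2.11.

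**The case against.** The plan deserves credit on several counts. It claims robustness only when one of the two models is wrong, and for the point estimate the check supports it: bias was between -0.011 and +0.003 whenever at least one model was right and all confounders were measured. It says that adjustment is for observed covariates, concedes selection bias, and plans balance and weight checks. The comparison with a randomised trial speaks of reducing bias, not removing it. All of this stands.

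A reader might infer three stronger things, and the documents do not support them. The first is that AIPW lacks the claimed property altogether; only the standard-error half fails, and the point-estimate half needs its conditions stated. The second is that the intervals will always be too narrow; no variance estimator is named, and with the outcome model wrong the usual standard error was too large in the stronger setting and about right in the weaker one. The third is that the plan should have included a check of interval coverage; that is shown for an estimator by simulation and is not a normal SAP item. The real gap is the unnamed variance method.

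It is also fair to say that the coverage shortfall is modest, that a stacked sandwich estimator is an alternative to the bootstrap, and that an E-value of 3.9 for the planned effect is not small. The number analysed is not fixed at 156 either: the plan prefers weighting because it keeps every participant in the analysis, which is why E-values are shown for both sample sizes.

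**Conclusion.** The statement about standard errors is wrong as written, and the statement about unbiasedness omits a condition it needs. Under the assumed settings, the influence-function standard error was about 12% too small with the propensity model wrong (7% in the weaker setting), about 6% too small with both models right (4-8% across the two tabulated settings), and about 5% too large with the outcome model wrong (no error in the weaker setting). Coverage ran from about 91% to 96%. These sizes depend on the simulation inputs and on the default standard error being the one used.

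This is a specification fault with a modest effect on the primary interval and a cheap remedy. The missing analysis of unmeasured confounding is secondary. It is worth adding because co-use is self-selected, but it would not carry the point alone.

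**What to change.** 1. Replace the sentence with: the AIPW estimate is consistent if at least one of the two models is correct and there is no unmeasured confounding.
2. State that the Week 12 standard error and confidence interval come from a bootstrap that refits the propensity and outcome models in each resample.
3. Optionally, report an E-value or similar bias analysis for the Week 12 estimate and its confidence limit nearest the null, beside the primary result. State the scale: the primary model is on log-odds and abstinence is common, so convert to a risk ratio from the model's standardised risks.

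The cost is a change of SAP wording, a small amount of programming and usually slightly wider intervals. No new data or participants are needed.

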3.0 Study Endpoints

Below is a table of the study endpoints and outcomes.

Type	Name	Time Frame	Brief Description
Primary	7-day point prevalence tobacco abstinence at the end of treatment (Week 12)	Final 7 days of treatment (Week 12)	7-day point prevalence abstinence from tobacco at the end of treatment (Week 12) will be assessed via biochemical verification and participant self-report and rates of abstinence will be compared between cannabis co-users and tobacco only controls.
Secondary	Changes in cannabis use during tobacco cessation treatment (among co-users)	Final 4 weeks of study treatment (Weeks 8-12)	Among cannabis co-users, cannabis use rates and amounts during the final 4 weeks of tobacco treatment (Weeks 8-12) will be assessed and

			nicotine dependence will be the primary model predictor.
Other: Exploratory	Cannabis co-use severity on tobacco cessation (among co-users)	Throughout trial participation	Tobacco abstinence and indicators of tobacco reduction (average cigarettes per day, quantitative cotinine, etc.) throughout the trial will be examined as a function of baseline cannabis use severity (determined by days of use in the past 30) to assess for dose-dependent impact on tobacco outcomes based on cannabis use severity.

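### The first-listed Aim 2 model uses only final-4-week cannabis use, so co-users lost earlier add no on-treatment data and dropout linked to cannabis use is not handled

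*Combined protocol and SAP*

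**What the plan says.** - **Lead model.** Section 10.0, Primary Study Aims, Aim 2: "generalized linear mixed effects models will be assessed with cannabis use rates and amounts during the final 4 weeks of treatment". Final-4-week use is named the main indicator and dependence group (medium/high against low) the main predictor. Section 3.0 lists this as the secondary endpoint, with time frame "Final 4 weeks of study treatment (Weeks 8-12").
- **All-weeks model.** The same Aim 2 text says that, once the end-of-treatment differences have been examined, "rates of cannabis use will be assessed by group (nicotine dependence severity) over all weekly study visits". Its stated purpose is to compare trajectories.
- **Baseline.** Section 10.0, Power and sample size: "Cannabis use during the final 4 weeks of study treatment as compared to baseline use will be assessed among co-users". Whether baseline enters the model as a covariate or as a response is not stated.
- **Power basis.** The same paragraph gives "139 in the cannabis co-use cohort (104 completers") and 80% power for a standardised difference of about 0.6.
- **Missing data.** Section 10.0, Missing data and attrition: "Methods of maximum likelihood yield valid inferences assuming ignorable attrition", which it explains as "attrition is accounted for by covariates or the dependent variable measured prior to dropout". The section promises an effort to keep assessing people who stop study procedures. It gives no imputation, weighting or sensitivity analysis.
- **Hypothesis 2 (Section 1.0).** Cannabis use is expected to rise in co-users with moderate to high dependence and to stay the same in those with low dependence. These are two within-group statements.

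**The concern.** A mixed model uses a person only through the outcome values that person contributes. When the outcome is restricted to the last four weeks, someone lost in Week 5 has no on-treatment value in the likelihood, although diaries for the lead-in and Weeks 1 to 4 have been collected. The missing-data section offers two ways for attrition to be ignorable: through covariates, or through earlier values of the outcome. The second works only if those earlier values are in the model, and in the lead test the on-treatment ones are not.

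Aim 2 asks whether stopping tobacco leads to more cannabis use. If co-users whose use climbs early are more likely to leave, the lead analysis loses the people who show the effect being sought. The observed change would then be too low in the medium/high group. It could also appear as a reduction in the low group, where the hypothesis expects none.

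**Working it through.** **1. The plan's own figures.** 139 × (1 − 0.25) = 104.25, so 104 completers and 139 − 104 = 35 not completing. With about 40% medium/high, the split of 104 is 42 and 62. The detectable difference (two-sided 5%, 80% power; two-sided is my assumption) is (1.960 + 0.842) × √(1/42 + 1/62) = 2.802 × 0.1998 = 0.56, which the plan rounds to 0.6. Power at exactly 0.6 is Φ(0.6/0.1998 − 1.96) = Φ(1.04) = 85%. The planned power figure therefore holds.

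**2. When the ignorability argument covers the lead model.**

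| Dropout depends on | Window-only model | Model on baseline and all weeks |
|---|---|---|
| nothing, or covariates in the model | covered | covered |
| baseline use | covered only if baseline enters the model (unstated) | covered |
| cannabis use observed during treatment | not covered | covered |
| cannabis use after the last observation | not covered | not covered |

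**3. Precision (illustrative).** The documents give no variances. Assumptions, in days of use per week: between-person SD 1.5 for level and 1.5 for change by Week 12; weekly noise SD 1; a linear rise to 1 day/week at Week 12 in the medium/high group and none in the low group; window taken as Weeks 9–12; 25% random dropout in Weeks 2–7. The window is centred at Week 10.5, so the true contrast is 10.5/12 = 0.875.

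- *Window only.* The variance of a person's window mean is 1.5² + (1.5 × 0.875)² + 1²/4 = 2.25 + 1.72 + 0.25 = 4.22, so the SD is 2.05 and the SE is 2.05 × 0.1998 = 0.41.
- *All weeks, same contrast.* Generalised least squares, with baseline means free in each group, gives SE 0.38. Power for 0.875 goes from 57% to 64%.
- *Change from baseline, completers plus baseline.* The variance is 1.72 + 0.25 + 1 = 2.97, so the SD is 1.72 and the SE is 1.72 × 0.1998 = 0.34. All weeks gives 0.32.

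**4. Bias (same assumptions).** Dropout log-odds rise by 0.5 to 1.0 per day/week of observed increase, with 25% lost per group.

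- *Same link in both groups.* Among those reaching the window, the mean change from baseline reads +0.67 to +0.52 in the medium/high group (true about +0.87) and −0.21 to −0.35 in the low group (true 0). The between-group contrast is nearly unbiased.
- *Link in the medium/high group only.* The contrast in final-4-week use reads 0.79 to 0.74 instead of 0.87–0.88. An all-weeks model gives 0.88.

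**5. A second set of assumptions, in standardised units.** Between-person variance is 0.6 plus a small random slope, within-person variance is 0.4, and about 25% drop out, driven by the previous week's use.

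| Link between use and dropout | True contrast | Window only | All weeks |
|---|---|---|---|
| none | 0.63 | 0.63 | 0.63 |
| same in both groups | 0.62–0.63 | 0.60–0.61 | 0.63 |
| medium/high group only | 0.63–0.64 | 0.47–0.52 | 0.63–0.64 |
| opposite in the two groups | 0.62 | 0.43 | 0.62 |

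Both sets agree: the contrast is sensitive to a differential link and little affected by a common one.

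**The case against.** - **The missing-data section also allows attrition explained by covariates.** This stands. A reader might infer that the maximum-likelihood argument cannot apply to the lead test at all. The text does not support that; the gap is limited to dropout linked to cannabis use during treatment.
- **Baseline may be in the model.** The power paragraph speaks of comparison with baseline. Entered as a response, baseline would bring early leavers back into the likelihood; as a covariate it would not. It is therefore too strong to say that early leavers contribute nothing. In either case, their on-treatment data remain unused.
- **The 104 completers are an attrition allowance.** This stands. The figure does not define an analysis set, and someone who leaves during the window still contributes partial data. Calling the lead test a completers analysis over-reads it.
- **Follow-up continues.** Section 9.0 says people who stop medication are still tracked, and Timeline Follow-Back fills missed diaries at weekly visits. This can reduce the loss. It is a collection effort rather than an analysis rule, and Sections 12.0 and 13.0 still provide for withdrawal.
- **The all-weeks model is already planned.** It is, which makes the change cheap. But it comes second and addresses trajectory.
- **The gain in power is small.** This stands. A reader might infer a large gain, because an SE near 0.30 can be obtained by forcing equal baseline means. Dependence groups are not randomised, and Section 2.0 (A2) reports that cannabis use is associated with greater nicotine dependence, so that constraint is not justified.

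**Conclusion.** The point holds in a limited form. The lead Aim 2 test ignores on-treatment data from co-users lost before the window, up to about 35 of 139, and the plan's missing-data argument does not protect it against dropout related to those data. The within-group changes are the most exposed: in the illustration they are about 0.2 to 0.35 day/week too low in both groups. The between-group contrast shifts by about 0.1 day/week (0.87 to 0.79–0.74) when the link exists in one group only, which is less than one third of its standard error. Under the second set of assumptions the shift is larger, from about 0.63 to 0.47–0.52.

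These sizes rest on assumed variances and dropout mechanisms. The documents supply neither, and give no evidence that rising cannabis use does drive dropout. The stated power for Aim 2 is not in error. For a secondary endpoint this is a worthwhile, low-cost improvement and not a defect that invalidates the aim.

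**What to change.** Keep final-4-week cannabis use as the target and change how it is estimated.

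- Fit one mixed model to the lead-in/baseline and all weekly cannabis data for all co-users. Include categorical week, dependence group, group-by-week terms and a person-level covariance structure. Let baseline means differ between dependence groups.
- Take the final-4-week group contrast and the within-group changes from baseline as model-based contrasts, and name this the primary Aim 2 test.
- Keep the window-only model as a sensitivity analysis.

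The cost is analysis wording: the daily diaries already run from the lead-in through Week 12. The downsides are that a time and covariance structure must be specified in advance, and that the model still assumes data are missing at random. A not-at-random sensitivity analysis would address the second.
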